Subjects with a clinical response after completion of treatment in either the Double-blind Acute Phase or the Open-label Acute Phase will be eligible to enter the Double-blind Maintenance Phase based on partial UC-DAI score (ie, without additional endoscopy).

Subjects without a clinical response after completion of acute treatment in the Open-label Acute Phase must be withdrawn.

All subjects will have a Screening Visit (Visit 1), and screened subjects who are eligible will proceed to the Baseline Visit (Visit 2). Study visits occur at the following time points after the Baseline Visit (Visit 2), dependent on the subject's partial UC-DAI score:

Double-blind Acute Phase: Week 2, Week 4, Week 8 (Double-blind Acute Phase Withdrawal)

Open-label Acute Phase: Week 2, Week 4, Week 8 (Open-label Acute Phase Withdrawal)

Double-blind Maintenance Phase: Weeks 2-4 (investigational product dispensation only), Week 13, Week 26 (Double-blind Maintenance Phase Withdrawal)

Inclusion and exclusion criteria:

Inclusion Criteria:

General:

1. Ability to voluntarily provide written, signed, and dated (personally or via a legally authorized representative [LAR]) informed consent or assent as applicable to participate in the study.
2. Subject's parent/LAR demonstrates an understanding, ability, and willingness to fully comply with study procedures and restrictions.
3. Male and female children and adolescents aged 5-17 years, inclusive, at the Baseline Visit (Visit 2).
4. Body weight 18-90kg at the Screening Visit (Visit 1) and the Baseline Visit (Visit 2).
5. Male, or non-pregnant, non-lactating female who agrees to comply with any applicable contraceptive requirements of the protocol or females of non-childbearing potential.
6. Diagnosed with mild to moderate UC, established by sigmoidoscopy or colonoscopy with compatible histology. Screened subjects may also have an unconfirmed diagnosis of mild to moderate UC; however, the diagnosis of mild to moderate UC must have been established by sigmoidoscopy or colonoscopy with compatible histology prior to the Baseline Visit (Visit 2).
7. Subject is able to swallow the investigational product whole.

Double-blind Acute Phase:

8. Partial UC-DAI score ≥ 2 (with a combined rectal bleeding **and** stool frequency score ≥ 1 **and** PGA=1 or 2) **and** with mucosal appearance (endoscopy score)=2 or 3 at the Baseline Visit (Visit 2), for which 5-aminosalicylic acid (5-ASA) would be used as part of normal treatment.

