Double-blind Maintenance Phase:

30. Mucosal appearance (endoscopic score)=2 or 3 based on central reading or local reading (if central reading is not available) at the Screening Visit (Visit 1) or Baseline Visit (Visit 2).

Re-randomization: Subjects with a clinical response, ie, partial UC-DAI \leq 1 (defined as rectal bleeding=0 **and** stool frequency \leq 1 **and** PGA=0) after completion of treatment in either the Double-blind or the Open-label Acute Phases will be eligible for re-randomization into the Double-blind Maintenance Phase provided they still meet all Baseline (Visit 2) inclusion and exclusion criteria (where re-assessed).

Note that an additional eligibility endoscopy is not required for entry into the Double-blind Maintenance Phase for subjects who achieve a clinical response after completion of treatment in either the Double-blind Acute Phase or the Open-label Acute Phase.

Subjects eligible for either the Double-blind Acute or the Double-blind Maintenance Phase can be re-randomized if they initially failed randomization for the following reasons: incorrect use of IVRS, late or missing central laboratory or endoscopy results, or other reasons of this type as long as they meet inclusion and exclusion criteria. Re-randomization can only take place after consultation with the medical monitor.

Subjects may be re-randomized into the Double-blind Maintenance Phase if they turned 18 during participation in either Acute Phase of the study.

Maximum duration of subject involvement in the study:

- Planned duration of screening period: 3 to 21 days
- Planned duration of treatment period: up to 42 weeks
- Planned duration of follow-up: 7 days

Endpoints and statistical analysis:

Primary Efficacy Endpoints

Double-blind Acute Phase:

The primary efficacy endpoint for the Double-blind Acute Phase is defined as the proportion of subjects with a clinical response (defined as partial UC-DAI ≤ 1 with rectal bleeding=0 **and** stool frequency ≤ 1 **and** PGA=0) at Week 8. This endpoint will be compared between treatment arms using a continuity-corrected chi-squared test.

Double-blind Maintenance Phase:

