Adverse events (AEs) will be coded using the Medical Dictionary for Regulatory Activities. Treatment-emergent AEs (TEAEs) will be defined in the statistical analysis plan. The number of events, incidence, and percentage of TEAEs will be presented by treatment arm (ie, low or high dose), and overall, by system organ class, and by preferred term. Treatment-emergent AEs will be further summarized by treatment arm for severity and relationship to investigational product. Treatment-emergent AEs related to investigational product, TEAEs leading to withdrawal, serious AEs, and deaths will be summarized by treatment arm.

Clinical laboratory tests and vital signs, and their changes from baseline will be summarized by treatment arm and visit.

Sample Size Justification

The sample size of 80 subjects originally selected for each of the Double-blind Acute and Double-blind Maintenance Phases was chosen based on both practical considerations and on agreement with the United States Food and Drug Administration.

STUDY SCHEDULES

Table 1: Double-blind Acute Phase

Table 1: Double-blind Acute Phase

Visit	1 (Screening)	Recommended Telephone call ^a	2 (Baseline)	3 ^b	3.1	3.2 ^{c, d, e, f}	6 ^g
Week/Month ^h	Day -21 to -3	Day -7 to -4	Week 0	Week 2	Week 4	Week 8/Withdrawal	Follow-up
█	✓					✓	
Review DUCS instructions, ability to read and understand e-diary with subject/caregiver	✓						
Subject/caregiver e-diary entry: rectal bleeding, stool frequency, DUCS, and Overall Current Health ^m	✓		✓	✓	✓	✓	
Assessment of e-diary compliance ^a		✓					
Global Change in Health ^l				✓	✓	✓	
IMPACT III ⁿ			✓			✓	
PUCAI (where applicable)			✓			✓	
Average stool frequency ^{o, p, q}			✓	✓	✓	✓	
Average rectal bleeding ^{o, p, q}			✓	✓	✓	✓	
PGAP ^{p, q}			✓	✓	✓	✓	
Endoscopy (flexible sigmoidoscopy or colonoscopy) for study eligibility ^{h, q, r}	✓		✓				
Endoscopy (flexible sigmoidoscopy or colonoscopy), where possible for subjects who are not entering into the Open-label Acute Phase) ^q						✓	
Calculate partial UC-DAI			✓			✓	
IRT entry	✓		✓	✓	✓	✓	

Table 1: Double-blind Acute Phase

Visit	1 (Screening)	Recommended Telephone call ^a	2 (Baseline)	3 ^b	3.1	3.2 ^{c, d, e, f}	6 ^g
Week/Month ^h	Day -21 to -3	Day -7 to -4	Week 0	Week 2	Week 4	Week 8/Withdrawal	Follow-up
Investigational product dispensed			✓	✓	✓	✓ ^s	
Investigational product collected and compliance calculated				✓	✓	✓	
Adverse events	✓	✓	✓	✓	✓	✓	✓
Concomitant medication	✓		✓	✓	✓	✓	✓

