Re-randomization (subjects entering Double-blind Maintenance Phase only)						✓	

Abbreviations: DUCS=Daily Ulcerative Colitis Scale for children and caregivers; eCRF=electronic case report form; e-diary=electronic diary; IRT= interactive response technology; PGA=Physician's Global Assessment; PUCAI=Pediatric Ulcerative Colitis Activity Index; UC-DAI=Ulcerative Colitis Disease Activity Index.

^a Approximately 4 to 7 days prior to the Baseline Visit (Visit 2) and prior to each subsequent visit (Visits 3, 3.1, and 3.2), it is recommended that site staff telephone the subject or the subject's caregiver to remind them to enter UC-DAI symptoms (rectal bleeding and stool frequency) into the e-diary every night, even if the subject has no symptoms.

^b Subjects may enter into the Open-label Acute Phase beginning at Visit 3 (after a minimum of 2 weeks double-blind treatment) and at any time until the end of the Double-blind Acute Phase provided all criteria have been met.

^c Subjects will continue into the Open-label Acute Phase if they have not met the criteria to enter the Double-blind Maintenance Phase and are eligible to continue into the Open-label Acute Phase.

^d Subjects will continue into the Double-blind Maintenance Phase if partial UC-DAI ≤ 1 (with rectal bleeding=0 *and* stool frequency ≤ 1 *and* PGA=0) *and* with mucosal healing (endoscopy score)=0 or 1, and are eligible to continue into the Double-blind Maintenance Phase.

^e This will be the final visit for subjects not entering the Open-label Acute Phase or the Double-blind Maintenance Phase.

^f The Baseline Visit (Visit 2) does not need to be repeated for subjects entering the Double-blind Maintenance Phase at the end of the Double-blind Acute Phase. Visit 3.2 will be considered the Week 0 visit for the next phase into which subjects are continuing.

^g Follow-up assessment in this phase applies only to subjects who are discontinuing the study; may be performed via telephone call within 7 days of the last dose of investigational product.

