^b Subjects will continue into the Double-blind Maintenance Phase if partial UC-DAI ≤ 1 (with rectal bleeding=0 **and** stool frequency ≤ 1 **and** PGA=0) and are eligible to continue into the Double-blind Maintenance Phase.

^c Subjects will be withdrawn from the study if they have not achieved a partial UC-DAI ≤ 1 (with rectal bleeding=0 **and** stool frequency ≤ 1 **and** PGA=0).

^d This will be the final visit for subjects not continuing into the Double-blind Maintenance Phase.

^e The Baseline Visit (Visit 2) does not need to be repeated for subjects entering the Double-blind Maintenance Phase at the end of the Open-label Acute Phase. Visit 4.2 will be considered the Week 0 visit for the Double-blind Maintenance Phase.

^f Follow-up assessment in this phase applies only to subjects who are discontinuing the study; may be performed via telephone call within 7 days of the last dose of investigational product.

^g A visit window of ± 3 days is permitted for all study visits.

^h The serum pregnancy test will be performed for all female subjects of childbearing potential at Week 8/Withdrawal (Visit 4.2). Urine pregnancy tests will be performed at all other visits.

ⁱ Rectal bleeding, stool frequency, DUCS, and Overall Current Health e-diary entry is completed once a day before bedtime every day for 5 days immediately prior to Visits 4, 4.1 and 4.2 of the Open-label Acute Phase.

^j The average stool frequency and rectal bleeding scores will be calculated and available to the investigator through a report from the e-diary provider.

^k Components of the partial UC-DAI.

^l Components of the modified full UC-DAI.

^m Only for subjects continuing into the Double-blind Maintenance Phase.

Table 3: Double-blind Maintenance Phase

Visit	1 (Screening) ^a	Recommended Telephone call ^b	2 (Baseline) ^a	5	5.1	5.2	6 ^c
Day/Month^d	Day -21 to -3	Day -7 to -4	Week 0	Weeks 2-4	Week 13	Week 26/ Withdrawal	Follow-up
Informed consent	✓						
Inclusion/exclusion criteria	✓		✓				
Demographics	✓						
Medical and medication history	✓						
Physical examination	✓				✓	✓	
Height	✓						✓
Weight	✓		✓				✓
Vital signs	✓		✓		✓	✓	
Biochemistry (includes C-reactive protein) and hematology	✓						✓
Pregnancy test (for females of childbearing potential only) ^e	✓		✓	✓	✓	✓	
Pharmacokinetic blood sampling (at participating sites only)						✓	
Urinalysis	✓					✓	
[REDACTED]				✓			
[REDACTED]	✓						
Stool sample (culture) ^{f,g}	✓						
[REDACTED]	✓					✓	

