4.3 Re-randomization

Subjects with a clinical response, ie, partial UC-DAI \leq 1 (with rectal bleeding=0 *and* stool frequency \leq 1 *and* PGA=0) after completion of treatment in either the Double-blind or the Open-label Acute Phases will be eligible for re-randomization into the Double-blind Maintenance Phase provided they still meet all Baseline Visit (Visit 2) inclusion and exclusion criteria (where re-assessed).

Note that an additional eligibility endoscopy is not required for entry into the Double-blind Maintenance Phase for subjects who achieve a clinical response after completion of treatment in either the Double-blind Acute Phase or the Open-label Acute Phase.

Subjects eligible for either the Double-blind Acute or the Double-blind Maintenance Phase can be re-randomized if they initially failed randomization for the following reasons: incorrect use of IVRS, late or missing central laboratory or endoscopy results, or other reasons of this type as long as they meet inclusion and exclusion criteria. Re-randomization can only take place after consultation with the medical monitor.

Subjects may be re-randomized into the Double-blind Maintenance Phase if they turned 18 years of age during participation in either Acute Phase of the study.

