7.1.2.3 Double-blind Acute Phase Week 8/Withdrawal (Visit 3.2)

The Double-blind Acute Phase Withdrawal Visit may occur at any time the subject discontinues participation in the Double-blind Acute Phase, or at completion of the study at Week 8 of the Double-blind Acute Phase. No additional Baseline Visit is required for subjects continuing into the Open-label Acute Phase or the Double-blind Maintenance Phase from this visit.

Subjects with a clinical response ie, partial UC-DAI ≤ 1 (with rectal bleeding=0 **and** stool frequency ≤ 1 **and** PGA=0) will be weighed and re-randomized into the Double-blind Maintenance Phase for treatment with low- or high-dose MMX mesalamine/mesalazine stratified by weight group based on current weight. Please see Section [6.2.3](#) for weight-stratified randomization groups. Subjects without a clinical response may continue into the Open-label Acute Phase and receive MMX mesalamine/mesalazine at the high dose for their weight group, based on their weight at Visit 3.2 (Week 8/Withdrawal of the Double-blind Acute Phase).

Collection of stool samples for all assessments must occur before administration of any bowel preparations for endoscopy if samples are collected on the same day as bowel preparation administration.

Endoscopy (flexible sigmoidoscopy or colonoscopy) should be performed at Visit 3.2 for subjects who are not entering into the Open-label Acute Phase. If performed, endoscopic video or photographs will be collected and sent to the study's central endoscopy reader for evaluation of mucosal healing. Please see a description of criteria used for endoscopic scoring in [Appendix 2](#). If endoscopy is not performed at Visit 3.2 and the subject is otherwise eligible, the subject may remain in the study.

Subjects and/or caregivers will have collected UC-DAI symptoms (rectal bleeding and stool frequency) via e-diary once a day before bedtime for 5 days prior to each study visit in the Double-blind Acute Phase. The average stool frequency and rectal bleeding scores will be calculated and be made available to the investigator through a report from the e-diary provider. The average stool frequency and rectal bleeding scores will be added to the PGA score determined by the investigator to calculate the partial UC-DAI. Please see a description of the PGA in Section [7.2.1.1](#) and the UC-DAI in Sections [7.2.1.1](#) and [7.2.1.2](#).

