7.1.3 Open-label Acute Phase

Subjects may enter the Open-label Acute Phase after completion of the Double-blind Acute Phase if they do not meet the requirements for entry into the Double-blind Maintenance Phase ie, they do not achieve a clinical response defined as a partial UC-DAI ≤ 1 (with rectal bleeding=0 *and* stool frequency ≤ 1 *and* PGA=0). This phase is intended to allow those subjects without clinical response in the Double-blind Acute Phase an additional 8 weeks to achieve clinical response at the high dose for their weight group. The subject's weight at Visit 3.2 (Week 8/Withdrawal of the Double-blind Acute Phase) will be used to determine the high dose assigned to the subject in the Open-label Acute Phase.

Subjects are also eligible for the Open-label Acute Phase provided they have participated in the Double-blind Acute Phase for a minimum of 2 weeks and, in the investigator's opinion, have not benefited from treatment in the Double-blind Acute Phase. In addition, they should not have experienced a possibly or probably related severe adverse event (AE) or a serious AE (SAE). Due to the delay in onset of action of 5-ASA preparations, investigators should make subjects/caregivers aware that they may not benefit from the investigational product within the first 2 weeks. Subjects who withdraw before Visit 3 will not be eligible for the Open-label Acute Phase.

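### Footnote d of the visit schedule requires an endoscopy score of 0 or 1 to pass from the Double-blind Acute to the Maintenance Phase, while the body text admits clinical responders without endoscopy

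*Protocol*

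**What the plan says.** Two rules for the step from the Double-blind Acute to the Maintenance Phase stand in current text.

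The schedule rule is footnote d of Protocol Table 1, repeated in SAP Table 5. It asks for clinical response (partial UC-DAI of at most 1, with its component conditions) and adds "with mucosal healing (endoscopy score)=0 or 1, and are eligible to continue into the Double-blind Maintenance Phase".

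The body-text rule is clinical response without a further endoscopy:

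- The Synopsis and Protocol Section 3.1 say that responders from either Acute Phase "will be eligible to enter the Double-blind Maintenance Phase based on partial UC-DAI score (ie, without additional endoscopy"). SAP Section 3.1 says the same.
- Protocol Section 4.3 and the matching Synopsis paragraph note that "an additional eligibility endoscopy is not required for entry into the Double-blind Maintenance Phase for subjects who achieve a clinical response". Section 4.3 makes re-randomisation subject to the Baseline criteria: "provided they still meet all Baseline Visit (Visit 2) inclusion and exclusion criteria (where re-assessed").
- Protocol Section 7.1.2.3 deals with the missing examination directly: "If endoscopy is not performed at Visit 3.2 and the subject is otherwise eligible, the subject may remain in the study".
- Protocol Section 7.1.3 opens the Open-label Acute Phase to subjects who "do not meet the requirements for entry into the Double-blind Maintenance Phase ie, they do not achieve a clinical response", which treats the two as the same thing.

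Two neighbouring entries matter. The Visit 3.2 endoscopy row of Table 1 reads "where possible for subjects who are not entering into the Open-label Acute Phase". Footnote b of Protocol Table 2 and SAP Table 6, which governs the step from the Open-label Acute Phase, ends "PGA=0) and are eligible to continue into the Double-blind Maintenance Phase" and has no mucosal condition.

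**The concern.** This is an entry rule that sites apply at a visit, and it stands in the table they are likely to consult at that visit. A site that follows footnote d would not re-randomise a clinical responder whom Sections 4.3 and 7.1.2.3 let in. A site that follows the body text would re-randomise the same child. At stake are which subjects reach the Maintenance Phase and by which route, and whether a child already in clinical response is sent to open-label high-dose treatment or leaves the study for want of an examination the plan calls optional. This is an internal inconsistency. No design choice is being criticised.

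**Working it through.** No figure in the plan needs reproducing. The check applies each rule to one case: a subject in clinical response at Week 8 of the Double-blind Acute Phase, otherwise eligible, with no Visit 3.2 endoscopy.

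1. **Body text.** Sections 3.1 and 4.3 need clinical response and no endoscopy, and Section 7.1.2.3 says the missing endoscopy does not end participation. Result: re-randomised into Maintenance.
2. **Footnote d.** It joins clinical response and a score of 0 or 1 with an *and*. There is no score. Result: condition not met.
3. **Can the entry endoscopy supply the score?** No. Inclusion criterion 8 requires a score of 2 or 3 for the Double-blind Acute Phase, and exclusion criterion 27 removes scores of 0 or 1. The score used for entry cannot satisfy footnote d, so a new endoscopy would be needed.
4. **Does the Section 4.3 qualifier reconcile the rules?** No. Baseline criteria apply there only where they are assessed again. With no endoscopy the mucosal criterion is not assessed again, so Section 4.3 still admits the subject and footnote d still does not.
5. **Where do the footnotes lead?** Footnote c of Table 1 sends a subject who has not met the Maintenance criteria to the Open-label Acute Phase, if eligible for it. Section 7.1.3 reserves that phase for subjects without clinical response, or with at least 2 weeks of treatment and no benefit in the investigator's opinion. A responder does not plainly fit either description. If the subject enters neither phase, footnote e makes Visit 3.2 the final visit.
6. **Comparison with the other route.** A responder from the Open-label Acute Phase with no endoscopy is admitted by Table 2 footnote b. The schedule therefore treats two unscoped responders differently according to the phase they come from, which the body text does not do.

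**Size.** The inputs are an expected 28 roll-overs from the two Acute Phases together and a Maintenance minimum of 80 (Protocol Section 9.6, SAP Section 3.5), and a target of endoscopy in about 30% of subjects at the end of the combined Acute Phases (Protocol Section 7.2.1.2).

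- The pool is 28/80 = 0.35, or 35% of the Maintenance minimum. The SAP keeps 28 although it reduces the Acute sample to 53.
- If *d* is the share of the 28 coming from the Double-blind Acute Phase and *s* is the share of those with a Visit 3.2 endoscopy, the number affected is 28 × *d* × (1 − *s*). The documents give neither *d* nor *s*. The formula runs from 0 (*d* = 0 or *s* = 1) to 28 (*d* = 1 and *s* = 0), so it does not size the problem.

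**Analysis.** The Maintenance primary analysis is a CMH test over three levels of Week 8 responder status (SAP Sections 5.8.1.2 and 8.2). A responder diverted to the Open-label Acute Phase who later enters from there would come in by the open-label route instead of the double-blind one.

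**The case against.** The strongest reply is that the answer is already in the plan. Section 7.1.2.3 addresses this very case, Section 4.3 is the section on re-randomisation, and the same rule recurs in the Synopsis and elsewhere. Against these stands one schedule footnote, copied into the SAP. Footnote d says subjects continue *if* the conditions hold, not *only if*, so it might be read as applying only where a score exists. Re-randomisation also runs through the IRT (Protocol Sections 6.2.1 and 6.2.2), and the documents do not show which entry rule the IRT enforces.

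Part of this stands. The body text is probably the intended rule, and how far practice would differ between sites is unknown. The *if* reading is weak, however, because the adjacent footnote c treats the Maintenance criteria as a gate, and footnote d is where Table 1 states them.

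A reader might also draw stronger conclusions that the documents do not support:

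- **That about 70% of Double-blind responders would be turned away**, because the endoscopy target is about 30%. The target covers all subjects at the end of both Acute Phases combined. Section 7.1.2.3 directs the Visit 3.2 endoscopy to those not entering open label, so the rate among responders may differ.
- **That all 28 expected roll-overs are at risk.** That figure includes the open-label route, where footnote b sets no mucosal condition.
- **That the Maintenance comparison is biased.** The entry decision precedes re-randomisation, so both arms are drawn from whichever subjects are admitted. SAP Section 8.2 defines Week 8 responder status by clinical response, so the definition of the strata does not depend on footnote d.
- **That the body text settles the case of a responder scoped at 2 or 3.** It does not do so clearly. Footnote d as worded would bar that subject, while Section 4.3 depends on what counts as re-assessed.

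**Conclusion.** The inconsistency is real, and footnote d is wrong as written in both documents for a clinical responder without a Visit 3.2 endoscopy. The schedule makes an optional examination a condition of entry, against every body-text statement of the roll-over rule. It bears on who enters the Maintenance Phase and by which route. It leaves the Acute primary endpoint and the validity of the randomised Maintenance comparison intact. The number affected cannot be stated from the documents. The conclusion assumes that the repeated and explicit body-text rule is the one the sponsor intends. If the footnote were intended, the body text would need changing instead. The point is worth correcting because the footnote, if followed, gives the wrong result for an individual child and the correction costs almost nothing.

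**What to change.** In footnote d of Protocol Table 1 and SAP Table 5, add that endoscopy is not required for entry, and that an otherwise eligible clinical responder with no Visit 3.2 endoscopy is re-randomised on partial UC-DAI alone, as in Protocol Sections 4.3 and 7.1.2.3.

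Adding this is better than deleting the mucosal clause. Deletion would also remove the schedule's only bar on responders scoped at 2 or 3 and so decide that case by default. The sponsor should state separately whether such a responder may enter Maintenance.

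Optionally, list the Double-blind Acute clinical responders who were not re-randomised, with their endoscopy status and recorded reason for discontinuation. Response and endoscopy scores are already planned in Listings 16.2.6.1 and 16.2.6.3. The listing should not attribute a cause, because the reasons named in Protocol Section 4.5.1 have no category for a missing endoscopy and such a case would probably sit under *Other*.

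The cost is a short addition to two footnotes, one separate decision by the sponsor and, if wanted, one listing. No new procedure is needed.
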